2.8.3.2 Vital signs

The following quantitative variables will be summarized by treatment, cohort, and visit: Body height (cm) in Cohorts 1-4, Weight (kg), head circumference (Cohort 5), Temperature (tympanic equivalent) (°C), Pulse (beats/min), respiratory rate (breaths/min), Systolic blood pressure (mmHg) and Diastolic blood pressure (mmHg).

Analysis in vital sign measurement using descriptive summary statistics for the change from baseline for each post-baseline visit will be performed. Change from baseline will only be summarized for patients with both baseline and post-baseline values and will be calculated as:

$$\text{Change from baseline} = \text{post-baseline value} - \text{baseline value}$$

The number and percentage of patients with newly occurring notable vital signs will be presented. Criteria for notable vital sign abnormalities are provided in [Table 2-8](#) and [Table 2-9](#) below.

A listing of all newly occurring or worsening abnormalities as compared with baseline will be provided, as well as a by-patient listing of all vital signs.

All patients level vital signs data will be listed.

Table 2-8 Criteria for notable vital sign abnormalities for age ≥ 18 years

Vital sign (unit)	Criteria
Systolic blood pressure (mmHg)	≥ 180 mmHg/≤ 90 mmHg with increase/decrease from baseline of ≥ 20 mmHg
Diastolic blood pressure (mmHg)	≥ 105 mmHg/≤ 50 mmHg with increase/decrease from baseline of ≥ 15 mmHg
Pulse (beats/min)	≥ 120 bpm/≤ 50 bpm with increase/decrease from baseline of ≥ 15 bpm
Respiratory rate	≥ 30 bpm ≤ 10 bpm
Temperature (°C)	≥ 37.5 (axillary) or ≥ 38.0 (other routes)
Weight	decrease > 10% from Baseline increase > 10% from Baseline

Table 2-9 Criteria for notably abnormal vital signs for age <18 years

Vital sign (unit)		Criteria	
Systolic blood pressure [mmHg]	High	≥ 95 th percentile of the age and height group ¹	
	Low	≤ 5 th percentile of the age and height group ¹	
Diastolic blood pressure [mmHg]	High	≥ 95 th percentile of the age and height group ¹	
	Low	≤ 5 th percentile of the age and height group ¹	
Body temperature [°C]	High	≥ 38°C (tympanic equivalent)	
	High	1-<6 months	> 160
		6-<12 months	>150
		12-<18 months	> 140
		18-<24 months	> 135
		2-<3 years	> 128
		3-<4 years	> 123
		4-<6 years	> 117
		6-<8 years	> 111
		8-<12 years	> 103
		12-<15 years	> 96
≥ 15 years	> 92		

Vital sign (unit)		Criteria
Pulse rate [bpm] ²	Low	1-<6 months <120 6-<12 months <110 12-<18 months < 103 18-<24 months < 98 2-<3 years < 92 3-<4 years < 86 4-<6 years < 81 6-<8 years < 74 8-<12 years < 67 12-<15 years < 62 ≥ 15 years < 58
Respiratory rate [breath per minute] ^{2,3,4}	High	1-<6 months >55 6-<12 months >50 12-<18 months > 46 18-<24 months > 40 2-<3 years > 34 3-<4 years > 29 4-<6 years > 27 6-<8 years > 24 8-<12 years > 22 12-<15 years > 21 ≥ 15 years > 20
	Low	1-<6 months <33 6-<12 months < 30 12-<18 months <28 18-<24 months < 25 2-<3 years < 22 3-<4 years < 21 4-<6 years < 20 6-<8 years < 18 8-<12 years < 16 12-<15 years < 15 15-18 years < 13
Weight	High	increase from baseline of ≥ 2 BMI-for-age percentile categories ⁵
	Low	decrease from baseline of ≥ 2 BMI-for-age percentile categories ⁵

bpm=beats per minute; NHLBI= National Heart, Lung, and Blood Institute;

¹ Fourth Report on Diagnosis, Evaluation and Treatment of High Blood Pressure in Children and Adolescents. Pediatrics 2004; 114; 555 (see section 5.6 for detailed computation)

² Fleming S, Thompson M, Stevens R, et al. Normal ranges of heart rate and respiratory rate in children from birth to 18 years of age: a systematic review of observational studies. Lancet 2011; published online March 15. DOI:10.1016/S0140-6736(10)62226-X.

³ Eldridge L. What is a Normal Respiratory Rate?, Updated May 16, 2014;

⁴ Kou .R., Shuei L., Bradypnea, Department of Physiology, School of Medicine, National Yang-Ming University, Taipei, Taiwan,

https://rd.springer.com/referenceworkentry/10.1007/978-3-540-29676-8_246

Vital sign (unit)	Criteria
⁵ BMI-for-age percentiles categories (P3, P5, P10, P25, P50, P75, P85, P90, P95, P97) are obtained from the WHO Growth Charts https://www.who.int/childgrowth/standards/bfa_boys_p_exp.txt https://www.who.int/childgrowth/standards/bfa_girls_p_exp.txt https://www.who.int/tools/growth-reference-data-for-5to19-years/indicators/bmi-for-age	

In addition to above analysis, for patients < 18 years of age, number and percentage of patients with increase or decrease from baseline of 1 BMI-for-age percentile category (See Table 2-11) will be provided by visit, cohort and treatment group.

The head circumference data will be analyzed descriptively only since it is not expected to change the values significantly within four weeks of the study.

2.9 Pharmacokinetic endpoints

Only cipargamin pharmacokinetics will be determined in this study.

PK parameters such as AUC_{inf}, AUC_{last}, AUC_{0-t}, C_{max}, C_{2min}, T_{max}, T_{1/2}, CL/F, and V_z are determined using non-compartmental method(s) and will be used for the analysis of PK.

Summaries of PK concentrations will be provided by cohort, treatment, and visit. PK concentrations below the limit of quantification (LLOQ) will be treated as zero in summary statistics and for geometric related mean and CV, concentrations below LLOQ will be included as half of the LLOQ value. Descriptive statistics of pharmacokinetic parameters will include arithmetic and geometric means, standard deviation (SD), coefficient of variation, (CV %), median, minimum and maximum, etc. CV% geo-mean will be calculated using this formula; (sqrt (exp (variance for log transformed data)-1))*100.

Two-sided 90% confidence intervals for the mean or geometric mean will be calculated by cohort and treatment group using normal or log-normal approximation as appropriate.

For those treatment groups that are selected for Cohorts 3-5, PK analysis will be provided by treatment group using all pooled Cohorts (1-5) as well as separately pooled Cohorts 3-5. When data from different cohorts are pooled, an IV cipargamin regimen in Cohorts 3 to 5 (aged < 12 years) will be analyzed together with the equivalent IV cipargamin regimen as used in Cohorts 1 and 2 (aged ≥ 12 years).

The pharmacokinetic parameters will also be listed by cohort, treatment and patient.

AAG

α -1-acid glycoprotein (AAG) data will be collected only for patients randomized to cipargamin. Summary statistics including geometric mean will be provided by visit, cohort and pooled cohorts also. The relationship between cipargamin exposure and AAG will be explored graphically using scatter plot including the regression line for cipargamin exposure on AAG. Scatter plot for cipargamin PK parameters and AAG will be provided by cohort and pooled. Listing will be provided by cohort, patient and visit.

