This will be an adaptive, multicenter, randomized, open label, sequential cohort study in participants aged ≥ 12 years old in Cohorts 1-2 and < 12 years old to ≥ 6 months in Cohorts 3-5 with a diagnosis of moderately severe and severe *P. falciparum* malaria (Section 16.4). This study is investigating the efficacy (parasite reduction and clinical outcome), safety, tolerability and pharmacokinetics of different injectable dose regimens of cipargamin in comparison to injectable artesunate. Cohort 1 includes only 18 participants aged ≥ 12 years old. As IV cipargamin has not yet been evaluated in patients with severe malaria, this first Cohort includes participants that are diagnosed with moderately severe malaria. Cohort 1 participants will have a minimum parasite count of 60,000 per µl and these high parasitemia levels will help to determine parasite clearance rates for the two dose regimen. In Cohorts 2-5 participants with severe malaria and a minimum parasite count of 5,000 per µl will be enrolled in an age-decreasing manner. This design aims at minimizing risks for pediatric participants < 12 years and at ensuring sufficient number of participants with severe malaria signs to evaluate their clinical improvement in the secondary endpoint. In all cohorts, participants on IV cipargamin arms will receive one daily injection of IV cipargamin over a minimum of 2 days and a maximum of 3 days; with IV artesunate as rescue medication. Participants in the IV artesunate arm will be administered a minimum of 3 doses during the first 2 days of treatment. Participants in all arms will receive Coartem bid for 3 days following IV therapy.

See sections [Section 6.1.1](#), [Section 6.1.2.1](#) and [Section 6.2.1](#) for details of each treatment arm.

Cohorts 1-2:

In Cohorts 1 and 2, 18 and 42 participants ≥ 12 years, who satisfy the inclusion/exclusion criteria will be randomized in the ratio 1:1:1 to one of three treatment arms. :

- IV cipargamin (KAE609) dose regimen 1
- IV cipargamin (KAE609) dose regimen 2
- IV artesunate

The two doses of IV cipargamin for Cohorts 1 and 2 have been selected based on the rationale described in [Section 4.2](#). The doses might be adjusted before the study start based on results obtained from the first in human (FIH) study in healthy volunteers to ensure exposure is maintained within the predicted safe and efficacious range (AUC_{0-24h} of 5-42 $\mu g \cdot hr/ml$) in the study participants.

Cohorts 3-5:

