4.2 Rationale for dose/regimen and duration of treatment

The primary aim of the intravenous antimalarial treatment in severe malaria is a rapid reduction of the initial parasite load. The efficacy of oral cipargamin in terms of parasite clearance has been demonstrated in previous studies using single doses between 10 mg and 150 mg. In study CKAE609A2202, aparasitemia was achieved by as early as 12 hours post-dose in the majority of the subjects treated with a single dose of oral cipargamin of ≥ 25 mg and by 24 hours post-dose in the majority of the subjects treated with oral cipargamin irrespective of dose. CCI

IV artesunate, the standard of care for severe malaria, has reported mean PRR₂₄ values between 7 and 43 across studies (Newton et al 2001, Nealon et al 2002, Newton et al 2003, Maude et al 2014). The CCI from four oral cipargamin studies including more than 150 participants with uncomplicated malaria (CKAE609X2201, CKAE609X2202, CKAE609A2201 and CKAE609A2202) is shown in Figure 4-1. In these studies, participants with baseline parasitemia of up to 60,000 parasites per μ l were included CCI oral cipargamin treatment. The full exposure-response relationship in participants with hyperparasitemia, as expected in severe malaria, remains to be elucidated.

In the same study CKAE609A2202, no safety concerns in patients with uncomplicated malaria were associated with CCI

The doses of IV cipargamin in this study have been selected in order not to exceed these mean exposures from the previous study.

The PK exposures of cipargamin following IV administration were predicted using a population PK model based on preliminary data from the first two cohorts of the ongoing phase 1 study CKAE609X2111. An adjustment in predicted exposures was made CCI (Silamut et al 1991) and the impact of CCI observed in studies in uncomplicated malaria and in healthy volunteers study, CCI CKAE609X2111.

Based on the above criteria, selected doses for Cohorts 1-2, i.e. 20 and 40 mg once every 24 hours, are expected to provide exposures within the safe and efficacious range. Due to the half-life of cipargamin of approximately 24 hours, cipargamin is expected to accumulate with daily

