6.1 Study treatment

6.1.1 Investigational and control drugs

Novartis will supply following study drugs (Investigational and control drug) as open label participant specific supplies as per [Table 6-1](#).

- Cipargamin (KAE609) 10 mg/ml and / or 15 mg/ml vial (investigational drug) for intravenous administration
- Artesunate 60 mg vials (control drug) for intravenous administration

Apart from Investigational and control drugs, Novartis will also supply additional treatments as rescue medication (Artesunate 60 mg vials) and oral medication as standard of care (Coartem 20/120 and 80/480 mg tablets).

Table 6-1 Investigational drugs, control drug and oral standard of care

Investigational/ Control Drug (Name and Strength)	Pharmaceutical Dosage Form and Packaging	Route of Administration	Supply Type	Sponsor (global or local)
KAE609 15 mg/ml	Solution for injection; 1 vial per box	Intravenous use	Open label	Novartis global
KAE609 10 mg/ml	Solution for injection; 1 vial per box	Intravenous use	Open label	Novartis global
Artesunate 60 mg/vial*	Powder for reconstitution; 1 vial per box	Intravenous use	Open label	Novartis global
Coartem® 20/120 mg**	Dispersible tablet; 6 tablets in a blister	Oral	Open label	Novartis global
Coartem® 80/480 mg**	Tablets; 6 tablets in a blister	Oral	Open label	Novartis global
*Control drug and rescue medication ** Oral medication as standard of care				

Dosing of study drugs for Cohorts 1-5 are described in below [Table 6-2](#):

Table 6-2 Dosing Regimen for IV cipargamin (KAE609) and IV artesunate

Cohort	Treatment arms	Dosing Regimen
1-2	IV KAE609 20 mg - dose regimen 1	Minimum of two doses; q24h (to be administered at 0 hour and 24 hours) and not exceeding three doses (Dose 3 at 48 hours) followed by oral medication (Coartem® bid for 3 days)

Cohort	Treatment arms	Dosing Regimen
1-2	IV KAE609 40 mg - dose regimen 2	Minimum of two doses; q24h (to be administered at 0 hour and 24 hours) and not exceeding three doses (Dose 3 at 48 hours) followed by oral medication (Coartem® bid for 3 days)
3-5	IV KAE609 - dose regimen 3	Minimum of two doses; q24h (to be administered at 0 hour and 24 hours) and not exceeding three doses (Dose 3 at 48 hours) followed by oral medication (Coartem® bid for 3 days). See Section 4.2 for process of dose selection for Cohorts 3-5

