6.1.2 Additional study treatments

6.1.2.1 Oral medication (standard of care)

All sites will receive Coartem as standard of care for oral treatment as per local practice. Following criteria are recommended for specified timepoints when switching participant from IV therapy to oral therapy as mentioned in below [Table 6-4](#):

First timepoint to switch participant from IV therapy to oral is at 48 hour. However, if a participant is not able to tolerate oral therapy then continue with IV treatments and evaluate again at 72 hour timepoint.

Table 6-4 Criteria for switch to oral medication (standard of care)

Time	Decision criteria	Decision
0 hours	Review screening results	Start dosing with IV therapy
24 hours	Assess rescue medication criteria	Continue IV therapy (and assess rescue medication criteria for participants on IV cipargamin) (see Section 6.2.1)
48 hours (Day 3) (1 st timepoint for a switch to oral therapy)	Assess the feasibility of administering oral medication	Start Coartem, if switch criteria are met as per label. Otherwise continue IV therapy (and assess rescue medication criteria per Section 6.2.1)
72 hours (Day 4) onwards	Assess the feasibility of administering oral medication at every 24 hours	Start Coartem, if switch criteria are met as per label. Otherwise continue IV artesunate or switch to IV artesunate therapy (for participants on IV cipargamin as per Section 6.2.1). Hospitalization should be extended till the time participant has not switched to oral therapy and assessments to be repeated as Day 4 if hospitalization is required beyond Day 4 (see Table 8-1 , Table 8-2)

Intravenous artesunate can be administered to a maximum of 7 days based as per supplied labels. Most participants after switching to oral therapy will be discharged from hospital with full oral course of Coartem for 3 days. Site to instruct participant (or participant's representative) on intake of oral therapy per label.

After switching to oral therapy (Coartem), if there are efficacy or safety concerns, the participant will be administered another ACT ([Section 6.2.1](#)) as per local treatment guidance.

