12.5.3 Pharmacokinetics

Only cipargamin pharmacokinetics will be determined in this study. For each cohort, cipargamin plasma concentration data will be listed by cohort, treatment, participant, and visit/sampling time point. Descriptive summary statistics will be provided by cohort (including pooled cohort), treatment and visit/sampling time point, including the frequency (n, %) of concentrations below the LLOQ and reported as zero.

Summary statistics will include mean (arithmetic and geometric), SD, CV (arithmetic and geometric), median, minimum and maximum. Concentrations below LLOQ will be treated as zero in summary statistics and for PK parameter calculations. For geometric related mean and CV, concentrations below LLOQ will be included as half of the LLOQ value.

Table 12-4 Non-compartmental pharmacokinetic parameters

AUClast	The AUC from time zero to the last measurable concentration sampling time (tlast) (mass x time x volume-1)
AUCinf	The AUC from time zero to infinity (mass x time x volume-1)
AUC0-t	The AUC from time zero to time t (e.g. 24h) (amount x time x volume-1)
Cmax	The maximum (peak) observed plasma, blood, serum, or other body fluid drug concentration after single dose administration (mass x volume-1)
Ct	Concentration at time t (mass x volume-1)
Tmax	The time to reach maximum (peak) plasma, blood, serum, or other body fluid drug concentration after single dose administration (time)
T1/2	The elimination half-life associated with the terminal slope (λ_z) of a semi logarithmic concentration-time curve (time).
CL/F	The total body clearance of drug from the plasma (volume x time-1)
Vz/F	The apparent volume of distribution during terminal phase (associated with λ_z) (volume)

Pharmacokinetic variables:

The following pharmacokinetic parameters will be determined using non-compartmental method(s) for IV cipargamin:

AUC_{inf}, AUC_{0-t}, C_{max}, C_{2min}, T_{max}, T_{1/2}, CL, and Vz.

Bio-fluid concentrations will be expressed in mass per volume units. All concentrations below the limit of quantitation or missing data will be reported as such in the concentration data listings. Concentrations below the limit of quantitation will be treated as zero in summary statistics.

The pharmacokinetic parameters will also be listed by cohort, treatment and participant.

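### In Cohorts 1–3, PK summaries after the 48 h pre-dose sample pool patients given two cipargamin doses with patients given three

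*SAP*

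**What the plan says.** **Dosing.** Protocol Table 6-2 (section 6.1.1) gives the cipargamin regimen as "Minimum of two doses; q24h (to be administered at 0 hour and 24 hours) and not exceeding three doses (Dose 3 at 48 hours"). Table 6-4 (section 6.1.2.1) sets the decision at 48 h: "Start Coartem, if switch criteria are met as per label. Otherwise continue IV therapy". Whether a patient gets dose 3 therefore depends on clinical state at 48 h. Protocol 6.2.1 allows rescue with IV artesunate at 24 h, and 9.1.1 stops study treatment on rescue, so some patients may have had one cipargamin dose only.

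**Accumulation.** Protocol 4.2 says: "Due to the half-life of cipargamin of approximately 24 hours, cipargamin is expected to accumulate with daily" dosing.

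**Sampling.** In Cohorts 1–3, Table 8-1 schedules PK at 48 h (pre-dose), 48 h 2 min, 49 h, 60 h, 72 h, Day 6 and Day 8. Its PK footnote covers all cipargamin participants and sets no condition on dose 3. SAP Table 5-9 gives these times separate analysis windows. In Cohorts 4–5 (Table 8-2) the last scheduled PK sample is the 48 h pre-dose one.

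**Summaries.** SAP 2.9: "Summaries of PK concentrations will be provided by cohort, treatment, and visit". Confidence intervals for means are by cohort and treatment group, with pooling over Cohorts 1–5 and 3–5. Protocol 12.5.3 uses the same grouping. Table 12-4 there defines AUCinf as "The AUC from time zero to infinity", and Cmax as the peak "body fluid drug concentration after single dose administration". SAP 2.4.1 tabulates the number of doses but does not link it to PK.

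**The concern.** A summary row such as the 72 h row in Cohort 3 mixes two populations. One is 48 h past its last dose and the other is 24 h past it, with an extra dose on board. The second group was selected because it could not yet take oral treatment. The pooled mean moves with the share of such patients and estimates the concentration of neither group. AUClast, and AUCinf if taken over the whole course, have the same problem.

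PK parameters and their correlation with alpha-1-acid glycoprotein (AAG) are secondary endpoints, and the protocol caps the number of doses because it expects accumulation. The later concentrations are where accumulation would show. AAG scatter plots that use whole-course AUC would carry a vertical spread that is only dose count. Comparisons between cohorts, and the pooled summaries, could be confounded if the dose-3 share differs between cohorts.

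**Working it through.** The documents give no figure to reproduce here, so the check is the size of the mixing.

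**Inputs.** Doses at 0 and 24 h, or at 0, 24 and 48 h (protocol Table 6-2). Half-life 24 h (protocol 4.2). Assumptions: equal IV bolus doses, one compartment, linear kinetics. Half-lives of 18 and 30 h were tried as an assumed range. The share f of patients given dose 3 is not stated and was varied.

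**Concentrations.** In units of the first-dose peak, C(t) = Σ exp(−k(t − tᵢ)), with k = ln 2 / 24 per hour. Let r be the fraction left after 24 h. Beyond 48 h every term decays at the same rate, so the three-dose to two-dose ratio is constant:

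(1 + r + r²) / (r + r²)

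- 24 h half-life: r = 0.5, ratio 1.75 / 0.75 = 2.33
- 18 h: r = 0.397, ratio 1.554 / 0.554 = 2.80
- 30 h: r = 0.574, ratio 1.904 / 0.904 = 2.11

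**AUC.** AUC(0–T) = Σ (1 − exp(−k(T − tᵢ))) / k over doses given before T; AUCinf is the number of doses divided by k.

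| Quantity (24 h half-life) | Two doses | Three doses | Ratio |
|---|---|---|---|
| 48 h pre-dose | 0.75 | 0.75 | 1.00 |
| 48 h 2 min | 0.749 | 1.748 | 2.33 |
| 60 h | 0.530 | 1.237 | 2.33 |
| 72 h | 0.375 | 0.875 | 2.33 |
| AUC0-24 | 17.31 | 17.31 | 1.00 |
| AUC0-48 | 43.28 | 43.28 | 1.00 |
| AUC to Day 8 (168 h) | 68.44 | 101.98 | 1.49 |
| AUCinf, whole course | 69.2 | 103.9 | 1.50 |
| Cmax, whole course | 1.50 | 1.75 | 1.17 |

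**Pooled arithmetic mean at 72 h**, equal to 0.375 + 0.5f:

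- f = 0.1: 0.425, which is 1.13 times the two-dose mean and 0.49 of the three-dose mean
- f = 0.5: 0.625, which is 1.67 times and 0.71
- f = 0.9: 0.825, which is 2.20 times and 0.94

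**One-dose patients.** For them the mixing starts after the 24 h pre-dose sample. Just after 24 h a one-dose patient is at 0.5 and a two-dose patient at 0.5 + 1 = 1.5.

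**The case against.** Much of the PK plan is untouched, and that part of the objection stands. The 48 h sample is drawn before any dose 3. AUC0-24 and AUC0-48 are the same in two-dose and three-dose patients. Cmax read literally from Table 12-4 is a single-dose peak, and even over the whole course it differs only 1.17-fold. Cohorts 4–5 have no later scheduled sample, although their last window in SAP Table 5-9 is open-ended, so a late draw could enter it. The endpoint is descriptive, with no hypothesis attached.

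It can also be said that the 48 h 2 min sample is listed among post-dose samples and so presumably requires an injection. The same footnote, however, lists 72 h as a pre-dose sample, when no cipargamin dose can follow. The labels therefore do not settle the matter. If these samples are skipped without dose 3, mixing between two-dose and three-dose patients starts at 60 h.

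Four stronger readings are tempting, and the documents do not support them:

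- **That CL and Vz are driven by dose count.** Correctly computed, they are normalised to dose and, like T1/2, do not depend on it under linear kinetics. Nothing says that the wrong dose would be used.
- **That exposure at dose 3 cannot be known.** Concentrations and parameters are listed per patient, dosing is recorded and population PK modelling is foreseen (protocol 4.2). Some analysis sections are redacted, so the absence of a split holds for visible text only.
- **That age comparisons are confounded.** The dose-3 share is given nowhere, overall or by cohort. Confounding is a possibility, not a finding.
- **That exposure on Day 3 breaches the target range.** Protocol section 3 wants doses set to "ensure exposure is maintained within the predicted safe and efficacious range" and labels that range, 5–42 µg·h/mL, as AUC0-24h. Part of the reasoning in section 4.2 is redacted, so whether accumulation was allowed for cannot be seen.

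**Conclusion.** The concern holds for Cohorts 1–3, for concentrations after the 48 h pre-dose sample, for AUClast, and for AUCinf if it is taken over the whole course. As grouped, these summaries describe neither two-dose nor three-dose patients. The gap is 2.33-fold for concentrations (2.11 to 2.80 over the assumed half-lives), 1.49-fold for AUC to Day 8 and 1.5-fold for whole-course AUCinf. These sizes rest on linear one-compartment superposition and the protocol's approximate half-life.

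The documents do not say to which dosing interval Cmax and AUCinf refer, so how far those two are affected is open. The primary and key secondary analyses are not involved. This is an inexpensive improvement to a stated grouping rule, and it should be made because readers of the study report will use the summary tables rather than the listings.

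**What to change.** 1. In SAP 2.9, present concentrations after the 48 h pre-dose sample, AUClast and whole-course AUCinf by number of cipargamin doses received (1, 2, 3). Identify any one-dose patients in the rows from 24 h 2 min onward. Mark dose count in AAG plots that use whole-course AUC.
2. State the dosing interval to which Cmax and AUCinf refer.
3. In Cohorts 1–3, report AUC24-48h and, for three-dose patients, AUC48-72h descriptively beside AUC0-24h, without judging them against a range defined for AUC0-24h.
4. Reconcile Table 8-1 and SAP Table 5-9 on whether the 48 h 2 min and 49 h samples are taken when dose 3 is not given.

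Items 1 to 3 need only SAP wording and extra table columns, and they use samples already scheduled. The downside is smaller groups per column, which matters most in Cohorts 1 and 2 with 6 and 14 patients per arm. SAP 1.1 describes those two cohorts as complete, so a sampling clarification under item 4 would help Cohort 3 at most, while the table changes apply to all three.
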